INDICATION:	Relapsed/refractory lymphomas (diffuse large B-cell, mantle cell, follicular, marginal zone, peripheral T-cell, small lymphocytic with large cell transformation, and Hodgkin lymphomas)
STUDY PHASE:	Phase I/II
BACKGROUND AND RATIONALE:	

Lenalidomide (Revlimid[®], CC-5013) is an oral immunomodulatory drug which has activity in several hematologic malignancies. Patients with relapsed/refractory lymphomas who failed multiple cytotoxic chemotherapy regimens were found to have encouraging overall response rates (over 30%) and duration of response (over 10 months) when treated with lenalidomide as a single agent.
 
We have previously reported the outcome of patients with relapsed/refractory lymphomas who continued to have residual hypermetabolic lesions on positron emission tomography (PET) scans after salvage chemotherapy and prior to ASCT (Svoboda et al. 2006, 211-216). We concluded that these patients have an extremely poor chance of durable remission after ASCT and should be considered for novel therapeutic approaches. Using lenalidomide maintenance therapy after ASCT in this setting is a novel concept which might improve the historically poor outcomes in this population.
	
STUDY OBJECTIVES:	
Primary:	
Determine the safety of lenalidomide maintenance therapy implemented early after ASCT and the appropriate dose for further studies.	
Secondary:	
Determine the progression free survival (PFS) and overall survival (OS) after ASCT in this high risk group with relapsed/refractory lymphomas treated with lenalidomide maintenance. We will compare these findings to our historical controls with PET positive disease prior to ASCT.	
STUDY DESIGN:	

We propose a phase I/II trial of lenalidomide maintenance therapy after ASCT in high risk patients with relapsed/refractory lymphomas. We define this group of patients by the presence of residual hypermetabolic lesion(s) on PET scans (PET positive disease) after salvage chemotherapy and prior to ASCT. This will be a non-randomized, single institution study.
 
Patients will be identified and undergo screening activity to determine eligibility within 28-100 days after ASCT following positive PET scan. Patients will be registered if determined to be eligible. Eligible patients will proceed with lenalidomide maintenance therapy.
	

Patients will continue on lenalidomide maintenance for 24 months unless they develop progressive disease or unacceptable toxicity. The initial dose of maintenance therapy will be 10 mg of lenalidomide daily. We plan to adjust the dose according to specific dose modification criteria. To monitor response during lenalidomide maintenance, we will obtain post-ASCT imaging scan prior to starting lenalidomide and then every three months during the first year and every 4 months during the second year.

STUDY ENDPOINTSPrimary:

Dose limiting toxicity (DLT) as assessed by NCI CTCAE version 4.0

Secondary:

Progression free survival

Overall survival

STUDY DURATION: 60 months

DOSING REGIMEN: The initial dose of lenalidomide will be 10 mg daily. We will use a 3+3 design to determine tolerability of this dose in these heavily pretreated patients. We will allow decreasing lenalidomide to 5 mg daily according to specific dose modification criteria. We will stop the study if there are 2 subjects with DLTs at the 5 mg dose level.

TOTAL SAMPLE SIZE: We plan to enroll 24 evaluable patients with relapsed/refractory lymphoma who will initiate lenalidomide maintenance after ASCT during the initial 3 years of the study. It is likely that at least 28 patients may be enrolled to provide 24 evaluable patients.

DRUG SUPPLIES: Celgene Corporation will provide lenalidomide at no charge through the Revlimid REMS® program for study participants.

2 Schedule of Study Assessments

Procedure	Screening	Cycle 1			Cycles 2-24*	Discontinuation From Protocol Therapy	Follow-Up Phase
	On day 28-100 after ASCT at hematological recovery (<28 days before starting maintenance)	Day 1 [^]	Day 15	Day 22	Day 1		Every 3 months ⁸
Informed Consent	X						
Record lymphoma diagnosis, current medications	X						
Record prior anti-cancer therapies	X						
Physical examination, vital signs, weight	X	X ⁶	X		X	X	
ECOG performance status	X	X ⁶	X		X	X	
Imaging (PET/CT or CT scan)	X				X ⁴		
ECG	X						
CBC	X	X ⁶	X	X	X	X	
Serum chemistries ¹	X	X ⁶	X		X		
Pregnancy testing ^{2,3}	X	X ⁶			X	X	
Register patient into Revlimid REMS® program	X						
Baseline lesion assessment	X						
Prescribe lenalidomide via Revlimid REMS® ⁷	X				X		
Response assessment ⁴					X ⁴	X ⁴	
Record adverse events			X		X	X ⁵	
Record concomitant therapies/procedures		X			X	X	
Assess drug compliance/patient's study calendar					X	X	
Follow-up anti-cancer treatments							X
Follow-up progression and survival information							X

* Variations of ± 7 days of scheduled visits are permitted; in rare circumstances, the study calendar may be recalculated to accommodate for a change in study visits out of this window (due to transportation issues, weather events, etc.) at the discretion of the treating physician.

[^] To be performed within 7 days of day 1 of lenalidomide therapy. If Screening physical examination, vital signs, weight, labs and ECOG performance status were done within 7 days of Day 1, they do not need to be repeated at this timepoint.

An unscheduled visit can occur at any time during the study. Source must be maintained for these unscheduled visits. The date for the visit and any data generated must be recorded on the appropriate CRF. Source documents for these unscheduled visits must also be maintained.

¹ To include Thyroid Stimulating Hormone (TSH) at Screening B, at treatment discontinuation, and whenever clinically indicated. T3 and T4 levels may be assessed as clinically indicated. If HIV and Hepatitis B status are unknown (unlikely since all patients undergoing ASCT are screened), then these tests will be sent at Screening B.

² Pregnancy tests for females of childbearing potential. A female of childbearing potential (FCBP) is a sexually mature female who: 1) has not undergone a hysterectomy or bilateral oophorectomy; or 2) has not been naturally postmenopausal for at least 24 consecutive months (i.e., has had menses at any time in the preceding 24 consecutive months).

³ Pregnancy tests must occur within 10 – 14 days and again within 24 hours prior to prescribing lenalidomide for Cycle 1 (prescriptions must be filled within 7 days). FCBP with regular or no menstruation must have a pregnancy test every 28 days while on therapy (including breaks in therapy); at discontinuation of lenalidomide, and at Day 28 post the last dose of lenalidomide. If menstrual cycles are irregular, the pregnancy testing must occur weekly every 14 days throughout the duration of lenalidomide treatment, including dose interruptions, at lenalidomide discontinuation, and at Day 28 following lenalidomide discontinuation (see Appendix A: Risks of Fetal Exposure, Pregnancy Testing Guidelines and Acceptable Birth Control Methods).

⁴ Progression will be determined by the treating physician as based on clinical picture and radiographic findings. The initial imaging will be performed after ASCT, but prior to initiating maintenance lenalidomide therapy. During the maintenance phase, imaging (PET/CT or CT scan) will be performed every 3 months during the first year and every 4 months during the second year of maintenance. Imaging studies after the second year of maintenance will be at discretion of treating physician. During the first cycle of maintenance therapy, there will be two visits with physical exam. Then, participants will be seen on day 1 of each subsequent cycle. It will not be required to document progression by tissue biopsy (it will be at discretion of treating physician).

⁵ An additional safety assessment will be done 28 days (+/- 7 days) following the last dose of protocol therapy.

⁶ If screening assessments were done within 7 days of Day 1, they do not need to be repeated at Study Day 1.

⁷ Lenalidomide must be prescribed through and in compliance with Celgene's Revlimid REMS® program. Prescriptions must be filled within 14 days, unless the patient is a female of childbearing potential, in which case the prescription must be filled within 7 days. Consideration should be given to prescribing lenalidomide 5 to 7 days in advance of Day 1 of each cycle to allow time for required patient and prescriber surveys, and drug shipment to patient. Any unused Revlimid® (lenalidomide) should be returned to the patient for disposition in accordance with the Revlimid REMS® program.

⁸ Subjects will be followed every 3 months for the first 3 years after discontinuation of protocol therapy, and then annually thereafter; those patients who did not achieve hematological recovery by Day 100 after ASCT and never started on lenalidomide maintenance will also be followed every 3 months for the first year and then annually for anti-cancer treatment and progression/survival information.

3 Background and Rationale

3.1 Introduction

For majority of lymphoma patients who relapse after complete response or who are primary refractory to initial treatment, a combination of salvage chemotherapy followed by high dose chemotherapy and ASCT is considered the standard of care. Sensitivity to salvage chemotherapy affects the outcome after ASCT (Philip et al. 1987, 1493-1498). Traditionally, the response to salvage chemotherapy prior ASCT was determined by conventional computed tomography (CT) scans using size criteria. In the past several years, it has been shown that functional imaging with PET scans using fluorodeoxyglucose (FDG) provides additional information to anatomic imaging with CTs. Recently, PET scans have been incorporated into the response assessment as published by the Imaging Subcommittee of International Harmonization Project in Lymphoma (Juweid et al. 2007, 571-578). These days, most institutions use 'PET/CT scans' which incorporate functional imaging with PET scan fused with low dose non-contrast enhanced CT scan.

We have previously reported the outcome of patients with relapsed/refractory lymphomas who continued to have residual FDG avid PET ('positive') lesions after salvage chemotherapy and prior to ASCT (Svoboda et al. 2006, 211-216). This group of patients included those who had excellent anatomic response by size criteria, but continued to have persistent hypermetabolic FDG activity within the residual lesions. We found that PET positive patients have an extremely poor chance of durable remission after ASCT. In the PET negative group, the median PFS was 19 months with 54% of patients without progression at 12 months after ASCT. In the PET positive group, the median PFS was 5 months with only 7% of patients without progression at 12 months after ASCT. We concluded that, for patients with PET positive residual disease after salvage chemotherapy and prior to ASCT, novel therapeutic approaches and agents need to be investigated.

Lenalidomide is a proprietary IMiD® compound of Celgene Corporation. IMiD® compounds have both immunomodulatory and anti-angiogenic properties which could confer antitumor and antimetastatic effects. Although the exact antitumor mechanism of action of lenalidomide is unknown, a number of mechanisms are postulated to be responsible for lenalidomide's activity against hematological malignancies. Lenalidomide has been demonstrated to possess anti-angiogenic activity through inhibition of bFGF, VEGF and TNF-alpha induced endothelial cell migration, due at least in part to inhibition of Akt phosphorylation response to bFGF (Dredge et al. 2005, 56-63). In addition, lenalidomide has a variety of immunomodulatory effects. Lenalidomide stimulates T cell proliferation, and the production of IL-2, IL-10 and IFN-gamma, inhibits IL-1 beta and IL-6 and modulates IL-12 production (Corral et al. 1999, 380-386). Up-regulation of T cell derived IL-2 production is achieved at least in part through increased AP-1 activity (Schafer et al. 2003, 1222-1232). The increased levels of circulating cytokines augment natural killer cell number and function, and enhance natural killer cell activity (Davies et al. 2001, 210-216).

Clinical activity of lenalidomide in various lymphoma subtypes has been documented in several phase II trials (Wiernik et al. 2008, 4952-4957; Witzig et al. 2009, 5404-5409; Habermann et al. 2009, 344-349; Boll et al. 2010, 480-482). In patients with relapsed/refractory mantle cell lymphoma, the overall response rate (ORR) was 53% with PFS at 12 month 40% (Habermann et al. 2009, 344-349). In patients with aggressive lymphoma (mostly diffuse large B-cell subtype), the ORR was 35% with PFS at 12 months about 25% (Wiernik et al. 2008, 4952-4957). There

also have been many case reports of patients who achieved durable complete response to lenalidomide after failing multiple cytotoxic chemotherapy regimens (Musuraca et al. 2010; Ivanov et al. 2010, 1758-1760).

Most clinical studies of lenalidomide in patients with active lymphoma used dose of 25 mg daily on days 1-21 in 28 day cycle which is the dosing recommended for active multiple myeloma. While lenalidomide was well tolerated in the lymphoma studies, the dose of 25 mg is associated with high risk of developing cytopenias including grade 3 neutropenia in 25-40% of patients and thrombocytopenia in 12-20% (Habermann et al. 2009, 344-349; Wiernik et al. 2008, 4952-4957). Our group reported that low dose lenalidomide at 10 mg daily (continuous dosing) in combination with weekly dexamethasone can be effective in patients with active relapsed/refractory low grade and mantle cell lymphomas (Ahmadi et al. 2009, 1700). The continuous dose of 10 mg daily has also been used in treatment of chronic lymphocytic leukemia/small lymphocytic lymphoma (Andritsos et al. 2008, 2519-2525).

Lenalidomide has been used as maintenance therapy in multiple myeloma, but there is limited experience with maintenance lenalidomide in lymphoma patients. Two large clinical trials of maintenance lenalidomide in patients with multiple myeloma after ASCT have shown benefit in PFS over observation. These studies used daily dosing of lenalidomide at 10 mg or 15 mg which were well tolerated over long term administration (Attal et al. 2010; McCarthy et al. 2010).

3.1.1 Indications and Usage:

Revlimid® (lenalidomide) is currently indicated for the treatment of patients with transfusion-dependent anemia due to Low- or Intermediate-1-risk myelodysplastic syndromes associated with a deletion 5q cytogenetic abnormality with or without additional cytogenetic abnormalities. Revlimid® is also approved in combination with dexamethasone for the treatment of patients with multiple myeloma that have received at least one prior therapy.

3.2 Adverse Events

The most frequently reported adverse events reported during clinical studies with lenalidomide in oncologic and non-oncologic indications, regardless of presumed relationship to study medication include: anemia, neutropenia, thrombocytopenia and pancytopenia, abdominal pain, nausea, vomiting and diarrhea, dehydration, rash, itching, infections, sepsis, pneumonia, UTI, Upper respiratory infection, atrial fibrillation, congestive heart failure, myocardial infarction, chest pain, weakness, hypotension, hypercalcemia, hyperglycemia, back pain, bone pain, generalized pain, dizziness, mental status changes, syncope, renal failure, dyspnea, pleural effusion, pulmonary embolism, deep vein thrombosis, CVA, convulsions, dizziness, spinal cord compression, syncope, disease progression, death not specified and fractures.

Complete and updated adverse events are available in the Investigational Drug Brochure and the IND Safety Letters.

3.3 Rationale for Treatment in this Setting

Our previously reported data and similar studies from other institutions indicate that patients with PET positive lesions after salvage chemotherapy and prior ASCT do very poorly (Svoboda et al. 2006, 211-216; Spaepen et al. 2003, 53-59). In our study, patients with residual PET positive lesions before ASCT had median PFS of 5 months with only 7% of patients without progression at 12 months after ASCT. It can be speculated that patients with PET positive lesions prior ASCT harbor chemotherapy resistant lymphoma cells in their tumors. Since the mechanism of action of lenalidomide differs from traditional cytotoxic chemotherapy, the use of this novel agent in this group of patients is an attractive concept. The immunomodulatory properties of lenalidomide over the maintenance period of 24 months could improve the overall outcome of patients following ASCT. Since there is a valid concern that lenalidomide could cause severe cytopenias when used early after ASCT, we proposed to administer dose 10 mg of lenalidomide daily with an option of dose modification to 5 mg daily according to previously defined toxicity criteria. The daily maintenance dosing of lenalidomide at 10 mg has been used in patients with multiple myeloma after ASCT and improved PFS in two large randomized trials (Attal et al. 2010; McCarthy et al. 2010).

4 Study Objectives and Endpoints

4.1 Objectives

4.1.1 Primary Objectives

- Determine the safety and dose-limiting toxicity of lenalidomide maintenance therapy implemented early after ASCT and the appropriate dose for further studies.

4.1.2 Secondary Objectives

- Determine the progression free survival and overall survival after ASCT in this high risk group with relapsed/refractory lymphomas treated with lenalidomide maintenance. We will compare these findings to our historical controls with PET positive disease prior to ASCT.

4.2 Endpoints (see Section 10.3 for definitions)

4.2.1 Primary Endpoints

- Dose limiting toxicity (DLT) as assessed by NCI version 4.0

4.2.2 Secondary Endpoints

- Progression free survival (PFS)
- Overall survival (OS)

5 Investigational Plan

5.1 Overall Design

Patients with relapsed/refractory lymphoma will undergo screening after ASCT following positive PET/CT scan. PET/CT scan results will be categorized as negative when no evidence of lymphoma is found by the radiologist at the time of the scan. PET/CT results will be categorized as positive when the intensity of any non-physiological signal is over 2.5 SUV, which is the measurement of FDG uptake often used to differentiate between benign and malignant lesions (Elstrom et al. 2003, 3875-3876; Al-Sugair and Coleman 1998, 303-319). Patients with diffuse bone marrow activity while on growth factors and with mild symmetric supraclavicular adipose tissue activity in the absence of focal lesions will be deemed as negative. All studies will be reviewed by a University of Pennsylvania nuclear medicine radiologist.

Patients with PET positive lesions who are candidates for ASCT as determined by their treating physician will undergo ASCT. The conditioning regimen will be at the discretion of the treating physician. Subsequent screening to determine eligibility will commence 28 to 100 days after ASCT at the time of count recovery defined as ANC \geq 1,000 and platelets \geq 60,000. Those patients who will undergo consolidative radiation after ASCT can proceed with maintenance treatment, but completion of their radiation and hematological recovery must occur by day 100 after ASCT.

To monitor response to lenalidomide, we will obtain post-ASCT imaging with PET/CT or CT scan prior to starting lenalidomide. During the lenalidomide maintenance, imaging (PET/CT or CT scan) will be performed at least every three months during the first year and at least every 4 months during the second year which reflects general frequency of imaging in this setting outside of this trial. Further imaging after 2 years of follow-up will be at discretion of the treating physician.

Patients will continue on lenalidomide for 24 cycles unless they develop progressive disease or unacceptable toxicity. One cycle is defined as 28 day period. We will initiate maintenance therapy with 10 mg of lenalidomide daily. We will dose adjust or hold lenalidomide for hematologic toxicity according to specific dose modification criteria.

[figure not shown]
The 3+3 design will be conducted as follows (see details in Section 10.4). The first 3 patients enrolled on our study must each be followed for 28 days on lenalidomide before enrolling the second group of 3 patients. If there is zero or one episode of dose limiting toxicity (DLT) in the initial group of 3 patients, then the group will be expanded to 6 patients at the 10 mg dose. If there are 2 or more DLTs in the initial group of 3 patients, then we will decrease the dose of lenalidomide to 5 mg daily and repeat the 3+3 design. If there is a second DLT in the expanded group of 6 patients at the 10 mg dose, then we will also decrease the dose to 5 mg and repeat the 3+3 design. We will stop the study if there are 2 or more DLTs at the 5 mg dose.

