5.3.5 Radiographic Evaluations

Subjects will undergo radiographic evaluations to assess disease status at the timepoints listed below. Timing of radiographic evaluations may be altered based on clinical indication or the discretion of the treating physician.

- PET/CT after at least 2 cycles of salvage chemotherapy, but prior ASCT (using separate PET scan and dedicated CT scan performed within one week is acceptable)
- Imaging (PET/CT or CT scan) after ASCT, but prior Cycle 1 of lenalidomide therapy
- Imaging (PET/CT or CT scan) every 3 cycles during the first year of lenalidomide maintenance therapy (near end of Cycles 3, 6, 9, 12)
- Imaging (PET/CT or CT scan) every 4 cycles during second year of lenalidomide maintenance therapy (near end of Cycles 16, 20, 24)

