5.5.3 Instructions for Dose Modifications or Interruption During a Cycle

Dose delay and dose reduction rules are as follows and in the table below.

- Lenalidomide dose reduction steps are outlined in Section 5.5.1.
- For treatment interruptions during a cycle, the 28-day schedule of each cycle will continue to be followed. Missed doses of lenalidomide are not made up.
- For treatment interruptions that delay the scheduled start of a new cycle, when toxicity has resolved as required to allow the start of a new cycle (Section 5.5.2), the restart day of therapy becomes day 1 of the next cycle.

Table 2: Dose Modifications :	
NCI CTC Toxicity Grade	Dose Modification Instructions (also see Instructions for Initiation of a New Cycle above)
Grade 3 neutropenia associated with fever (T ≥ 38.5° C) or Grade 4 neutropenia	
 • Hold (interrupt) lenalidomide dose. • Follow CBC weekly. • If neutropenia has resolved to ≤ grade 2 prior to Day 28 of the current cycle, restart lenalidomide at next lower dose level and continue through the scheduled Day 28 of the current cycle. Otherwise, omit for remainder of cycle and reduce the dose of lenalidomide by 1 dose level at the start of the next cycle. Omitted doses are not made up. If neutropenia is the only toxicity for which a dose reduction is required, G-CSF may be used and the lenalidomide dose maintained.
Thrombocytopenia ≥Grade 3 (platelet count < 50,000/mm³)	
 • Hold (interrupt) lenalidomide dose. • Follow CBC weekly. • If thrombocytopenia resolves to ≤ grade 2 prior to Day 28 of the current cycle, restart lenalidomide at next lower dose level and continue through the scheduled Day 28 of the current cycle. Otherwise, omit for remainder of cycle and reduce the dose of lenalidomide by 1 dose level at the start of the next cycle. Omitted doses are not made up. • Hold prophylactic anti-coagulation, if applicable. • Restart prophylactic anti-coagulation when platelet count is ≥ 50,000/mm³.
Non-blistering rash	
 • If Grade 3, hold (interrupt) lenalidomide dose. Follow weekly. • If the toxicity resolves to ≤ grade 1 prior to Day 28 of the current cycle, restart lenalidomide at next lower dose level and continue through the scheduled Day 28 of the current cycle. Otherwise, omit for remainder of cycle and reduce the dose of lenalidomide by 1 dose level at the start of the next cycle. Omitted doses are not made up.
Grade 3	

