6.4 Adverse Event Updates/IND Safety Reports

Celgene shall notify the Investigator via an IND Safety Report of the following information:

- Any AE that is possibly, probably or definitely associated with the use of drug in this study or in other studies that is both serious and unexpected.
- Any finding from tests in laboratory animals that suggests a significant risk for human subjects including reports of mutagenicity, teratogenicity, or carcinogenicity.

The Investigator shall notify the University of Pennsylvania IRB promptly of any new serious and unexpected AE(s) or significant risks to subjects that meet the local reporting policy.

The Investigator must keep copies of all AE information, including correspondence with Celgene and the IRB on file (see Section 11.4 for records retention information).

7 Response Assessment

Baseline lesion assessments must occur within ≤ 28 days of protocol therapy initiation or as indicated in Section 2, Schedule of Study Assessments.

Efficacy assessments are scheduled to occur within 28 days prior to starting lenalidomide therapy, every three cycles during the first year, and every four cycles during the second year of study participation. Clinical assessments, including laboratory studies and physical exams, will occur monthly throughout study participation. Follow-up contact with the subjects should occur at a minimum of 3 months during the three years after finishing maintenance phase and annually after that. The frequency of follow-up imaging after completing 24 cycles of lenalidomide maintenance will be at discretion of the treating physician.

8 Protocol Amendments and Deviations

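### Imaging is set by calendar in 5.1 but by treatment cycle in 5.3.5, so scan dates, and with them recorded progression, can depend on toxicity delays and physician choice

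*Combined protocol and SAP*

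**What the plan says.** The plan states the imaging schedule in two ways.

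- **By calendar.** Section 5.1: "imaging (PET/CT or CT scan) will be performed at least every three months during the first year". Section 2 footnote 4: imaging "will be performed every 3 months during the first year and every 4 months during the second year of maintenance". The synopsis has the same month-based intervals.
- **By cycle.** Section 5.3.5: imaging "every 3 cycles during the first year of lenalidomide maintenance therapy", placed near the ends of Cycles 3, 6, 9 and 12, then of Cycles 16, 20 and 24. Section 7: "every three cycles during the first year, and every four cycles during the second year of study participation".

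Three further provisions decide whether these agree in practice.

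- Under 5.5.2 a cycle does not start until toxicity has resolved. Under 5.5.3, when that delays a cycle, "the restart day of therapy becomes day 1 of the next cycle". A hold within a cycle leaves the 28-day clock running.
- Section 5.3.5 adds: "Timing of radiographic evaluations may be altered based on clinical indication or the discretion of the treating physician". It gives no window and no limit.
- Section 2 footnote * says that, in rare circumstances, "the study calendar may be recalculated to accommodate for a change in study visits out of this window".

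Section 10.3 runs PFS from transplant to first documented progression or death. Footnote 4 has the treating physician determine progression from the clinical picture and imaging. No section says which clock governs, and 10.3 and 10.6 give no rule for progression first found at a late scan.

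**The concern.** In a maintenance trial, radiographic progression gets its date from the scan that finds it. If that scan is tied to a cycle end, a patient whose counts delay the next cycle is also scanned later. Such delays are foreseeable: 3.3 raises severe cytopenia early after transplant as a concern. Entry requires platelets of about 60,000, and a new cycle requires 50,000.

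The physician who determines progression may also move the scan. Assessment timing is then not independent of treatment tolerance or of clinical impression. PFS is a secondary endpoint, but 10.1 makes it the purpose of phase II, and 10.6 rests the judgement of success on PFS at 12 months (PFS12). A single-arm trial has no concurrent group in which the same slippage would cancel out.

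**Working it through.** **The plan's own figures.** Section 10.6 calls success at more than 4 of 24. Exact binomial:
- P(X ≥ 5 | 24, 0.10) = 0.0851 (stated 0.09).
- P(X ≥ 5 | 24, 0.30) = 0.8889 (stated 89%), so the false negative rate is 0.1111 (stated 0.11).

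All reproduce, and none depends on the scan schedule.

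**The two clocks.** A cycle is 28 days (5.1); a month is taken as 365.25/12 = 30.44 days.
- Year 1: 3 × 28 = 84 days against 3 months = 91.3 days, so about 7 days of slack.
- Year 2: 4 × 28 = 112 days against 4 months = 121.75 days, so about 10 days of slack.

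**Effect of delayed cycle starts on one year-1 interval.** Section 5.7 ends treatment at 28 or more consecutive days off drug, so one delay can last at most 27 days.
- 7 days: 84 + 7 = 91, still within three months.
- 14 days: 84 + 14 = 98 days (3.2 months).
- 27 days: 84 + 27 = 111 days (3.6 months).
- Extreme cases: 84 + 2 × 27 = 138 days in the first interval (two cycle starts after Cycle 1 Day 1) and 84 + 3 × 27 = 165 days in a later one (three starts).

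**Effect on recorded PFS time.** Assume that progression is found only at scans and arises uniformly within the interval. The mean detection lag is then half the interval: 42 days with no delay, 49 with a 14-day delay, 55.5 with 27 days. The rise is half the delay (7 and 13.5 days) and occurs only in the interval containing it.

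This is the upper end. Against the undelayed scan dates, a 14-day delay records progressions from the first 84 days 14 days later. Those arising in the next 14 days are found at day 98 of the interval instead of day 168, which is 70 days earlier. The net mean shift is (84 × 14 − 14 × 70)/98 = 2 days. For 27 days it is (84 × 27 − 27 × 57)/111 = 6.6 days.

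**Effect on PFS12.** Assume constant hazard with a true PFS12 of 10%, so S(t) = 0.10^(t/365), and detection only at scans. The recorded PFS12 is then S at the last scan on or before day 365. With a 14-day delay in the first interval:
- Start on day 100: the third scan moves from 100 + 252 = 352 to 366. The last scan before day 365 becomes day 282. Recorded PFS12 rises from S(352) = 10.9% to S(282) = 16.9%.
- Start on day 64: the third scan moves from 64 + 252 = 316 to 330. Recorded PFS12 falls from S(316) = 13.6% to S(330) = 12.5%.

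With start days spread evenly over days 28 to 100 and every patient delayed in the first interval, the average recorded PFS12 is 13.6% with no delay, 12.7% with 14 days, 12.9% with 27 days and 13.2% with 54 days. Under these assumptions delay does not raise the average.

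**The case against.** The strongest reply is that this is a wording mismatch with little consequence.

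- Three cycles already satisfy 5.1 with about a week to spare, and the two sections can be read together with 5.1 as the floor. That reading is possible, but no section states it, and a site following 5.3.5 as written can breach it.
- Holds within a cycle do not move scans. The 28-day limit counts consecutive days off drug, so a 27-day delay requires that no hold was running when the preceding cycle ended. This stands; 138 and 165 days are corner cases.
- Detection is not by scan alone. Footnote 4 allows progression on the clinical picture, visits occur each cycle, and 5.5.2 requires weekly evaluation during a delayed start. This stands and reduces the lag.
- Footnote * is confined to rare circumstances such as transport or weather, so it adds little. The discretion in 5.3.5 is the real opening, and it can bring scans forward as well as put them back.

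A reader might infer more: that progression is always dated later, that the error favours lenalidomide over the historical rate, and that the 0.09 false positive rate is therefore inflated. The documents do not support this. Some progressions are found earlier on the shifted dates, and average recorded PFS12 falls slightly in the check above. The documents do not give the scan schedule of the historical patients, and 5.1 describes trial imaging as matching usual practice. The frequency of delays is not given.

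**Conclusion.** The point holds as an inconsistency with a bounded effect. Two imaging clocks are in force with no order of precedence. They part once cycle-start delays within a year-1 interval exceed about 7 days, and timing is also open to the treating physician's discretion.

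Recorded progression can therefore depend on toxicity and physician choice. Under uniform progression and scan-only detection, mean recorded PFS for progressions arising in the affected interval lengthens by at most about half the delay: 7 days for a 14-day delay and 13.5 days for a 27-day delay. Clinical detection makes it less. An individual patient can be recorded later by the whole delay.

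The direction of the effect on PFS12 depends on start day, and its net size cannot be fixed without the frequency of delays. No net inflation of the false positive rate is claimed. Alpha, power and N stand as stated. This is a cheap improvement, not a flaw that undermines the design.

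**What to change.** - In 5.3.5, set the existing intervals (84 days in year 1, 112 days in year 2) as calendar dates counted from Cycle 1 Day 1 with a window of +/- 7 days, regardless of holds or delayed cycles. Departures then do not accumulate from one scan to the next.
- Allow earlier or additional scans when clinically indicated. Record any late or missed scan as off-schedule, with the reason.
- Align the synopsis, 5.1, Section 2 footnote 4 and Section 7 with that one schedule.
- In 10.6, add a sensitivity analysis of PFS and PFS12 in which progression first found at a late scan is interval-censored between the last progression-free scan and the detecting scan. Dating it to the scheduled scan should be shown only as a conservative bound, because it also backdates disease that arose after that date.

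The cost is protocol wording, a log of off-schedule scans and one further analysis. It adds no scheduled scans and changes no dosing rule. The downside is that scans and cycle visits may fall on different days for patients with delayed cycles.
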